4.2.2 Exclusion criteria

Patients whose CFTR modulator status is unknown or only have one year of CFTR data recorded on the registry will be excluded from the analysis of the effects of CFTR modulators. This is to account for the fact that DIOS data is annualised on the registry, therefore there is no certainty at what time of year DIOS was diagnosed in relation to commencing CFTR modulatory therapy.

Expected duration of participant participation

No individual participant interaction. The CFTR MAGIC study will take place over 24 months, from 1/10/2021 to 30/9/2023.

Participant Withdrawal

Not applicable – no individual participant involvement.

Informed consent

PwCF have given explicit consent to their usual CF teams for their demographic, clinical care, and health outcomes data to be submitted to either the UK or US CF registries.^{15, 16} Written consent is gained from pwCF or their parent/ legal guardian and as part of this they are made aware that the information may be used for research and to plan and improve the quality of clinical care. For the UK CF Trust the use of any data from the registry requires the approval of the Registry Steering Committee.¹⁵ In the US, the request for registry data is reviewed and approved by the Patient Registry/Comparative Effectiveness Research Committee. The project has received approval from both the US and UK registries for patient data to be released to be used for this project. Data is released by the registries as anonymised forms of the data to maintain patient confidentiality. Additional patient specific consent for CFTR MAGIC is therefore not required.

DATA COLLECTION REGIMEN

No new data collection will be necessary within this project. Existing data will be provided by the US and UK CF registries. Requests for the data was approved by the UK CF Trust Registry Steering Committee after reviewing the programme development grant aims, statistical analysis and plan for publication of results. In the US, the request for registry data was reviewed and approved by the Patient Registry/Comparative Effectiveness Research Committee and was subject to peer review. Data will be provided as anonymised data so the individuals cannot be identified and analysed using Stata software.

ACCESS TO REGISTRY DATA

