Data will be in the form of registry data provided from the US and UK CF registries from the period 2007-2017. These datasets will be provided as encrypted data via the registries preferred data sharing platform (Box.com or similar). Both registries have already reviewed and approved the sharing of their data for use within this project.

Criteria for terminating the registry data

No data will be archived in a data repository following project completion due to the requirements of the CF Foundation and CF Trust registries. The CF foundation considers the project to be completed after 3 years. After this time data files and any copies of the files will be destroyed. The CF Foundation will be provided with written confirmation of destruction of the data and completion of the project or alternatively provided with a sufficient justification for continuation of the project if required. The CF Foundation maintains copies of all data sets sent to researchers and can provide the data again if required for auditing purposes. The CF Trust requires all data to be destroyed at the end of the project and that all data forms must be permanently destroyed within 12 months of the date of supply unless approval has been granted by the UK CF Registry Research Committee for an extension.

STATISTICAL ANALYSIS

Data will be provided from the UK and US registries as an encrypted file and analysis will be performed using Stata software. Statistical analysis will be completed by members of the research team, led by [name]. A full plan for statistical analysis is described below.

[figure not shown]
Objective 1: Assess the rate of PERT use and the incidence of DIOS in UK and US registries 2007-2017

1. Descriptive analysis 2007-2017 to include:
 - Yearly cumulative incidence of DIOS and prevalence of PERT usage in the UK and US (2007-2017)
 - PERT use will be dichotomised (i.e use/no use)
 - Incidence of DIOS (event/no event)
 - **Plotted by year**, separated by registry
 - Stratification by age range (<6, 6-11, 12+)

- Patient demographics of DIOS and PERT reporting
 - The distribution of yearly reported incidence events and use prevalence (%) will be addressed according to age groups, sex, BMI, ethnicity, antibiotic use, comorbidities (including Pseudomonas colonisation, GI complication history, GI co-morbidities such as CFRD and CFRLD), FEV₁ lung function, centre (where available, pseudo ID).

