Trends in the registries will be described, however no statistical tests will be used to directly similarities and differences between the registries over time due to the distinctions between the two registries.

2. The patient demographics lists above will be used for demographic propensity matched controls
 - Patient-level data will be used to create registry-based control groups with similar demographic features to those taking CFTR modulators. Due to the restricted genotype eligibility criteria for the earliest CFTR modulator, Ivacaftor, the CFTR user group may have distinct features compared to the overall registry. In addition the restrictive indications for the use of Ivacaftor and limited number of DIOS events on the registry will therefore mean the number of events within exposed individuals may be low. Therefore propensity scores will be used to define a control group of non-eligible non-users that are otherwise representative at the year CFTR modulator exposure was commenced. See directed acyclic graph (DAG) below.
 - Nearest neighbour matching, caliper 0.2 standard deviation, 3:1 ratio of unexposed to exposed will be used for propensity matching. Matching will be performed according to first year of exposure using all pre-exposure information in wide format. Standardised mean difference will be used to check covariate balance between matched and unmatched populations. Average treatment effect of treated will be used to assess matching specification with alternates.

Directed acyclic graph (DAG) for the potential relationship of CFTR modulator and DIOS

Objective 2: Determine the effect of CFTR modulators on DIOS and PERT, using an population-level controlled interrupted time series

This protocol is confidential and the property of the University of Nottingham. No part of it may be transmitted, reproduced, published, or used by others persons without prior written authorisation from the University of Nottingham

Objective 2 will investigate the effect of CFTR modulator intervention on the rate on PERT use and DIOS incidence.

We will test the hypotheses that;

- a) Ivacaftor introduction (2012) in patients with gating mutations lowered the rate of PERT use and the incidence of DIOS in both registries, and that
- b) The introduction of Orkambi (Ivacaftor/Lumacaftor) for those homozygous for F508del mutations in the US (2015) lowered the rate of PERT use and the incidence of DIOS. Specifically, we hypothesise a downward trend, no lag.

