Hypothesis 2b will be explored in the US population only given that introduction of Orkambi was delayed in the UK until 2019.

ITS will explore proportion of DIOS events at population level in the CFTR modulator population and the propensity score defined comparator population. ITS will explore proportion of overall PERT usage (user/non user), and the proportion of individuals with a reduction in weight standardised PERT dose (decrease/no decrease)

- Sensitivity will include distributed lag of 1-3 (years) to account for the possibility that exposure time in the first year was not sufficient for a change in outcome, compared to non-lagged, and to explore PERT usage status change to non-user.
- Autoregression will be visually assessed and effects will also be compared with those from autoregressive model (Prais-Winsten).

Analysis will be performed overall and stratified by 1) Age group (<6, 6-11, 12+) to account for clinical distinctions in pre-schoolers, school age children and adults, 2) History of meconium ileus, as these individuals are at higher risk of DIOS events.

Analysis of hypothesis 2a: Controlled interrupted time series: ivacaftor analysis in G551D criteria

- Segmented regression (with and without lag term), and Prais-Winsten regression for serial correlation.
- Impact model: downward trend (no/minimal level change)
- Model includes: pre intervention, level change, post intervention: interaction with covariates (age, gender, disease status).
 - Pre intervention: no CFTR modulator (time control)
 - Post intervention: ivacaftor (minimum 6 months)
 - US 2007-2011:2012-2017
 - UK 2007-2011:2012-2017
- Propensity score matched controls (demographic control)

Analysis hypothesis 2b. Interrupted time series: lumacaftor/ivacaftor analysis in US F508del subgroup.

- Hypothesis, downward trend no lag.
- Pre intervention no CFTR modulator: (time control)
- Post intervention: lumacaftor/ivacaftor, minimum 6 months
 - US 2007-2014:2015-2017
- Propensity score matched controls (demographic control)

- Parallel plot of UK F508del homozygous subgroup (indirect genotype control)

Objective 3: Determine the effect of CFTR modulators on DIOS and PERT: patient-level time series

This will focus on patient level associations to complement the registry level findings. We will specify explore associations in the incidence of PERT usage and DIOS events between 2012 and 2017 in individuals with CFTR modulators, compared to propensity matched controls.

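### US hypothesis 2a does not say how matched controls who start lumacaftor/ivacaftor from 2015 are handled, and carrying them forward as untreated would pull the slope contrast toward no effect

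*Combined protocol and SAP*

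**What the plan says.** Statistical Analysis, Objective 1, item 2 uses propensity scores to "define a control group of non-eligible non-users that are otherwise representative at the year CFTR modulator exposure was commenced". The preceding sentences concern the genotype restriction on ivacaftor, so that is the eligibility meant. On timing, the plan adds: "Matching will be performed according to first year of exposure using all pre-exposure information in wide format".

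The matching characteristics come from the descriptive list in item 1, where outcomes "will be addressed according to age groups, sex, BMI, ethnicity, antibiotic use, comorbidities" and further items such as lung function and centre. Genotype is not on that list. The reference to all pre-exposure information, and the DAG (not shown), leave its role open.

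Under Objective 2, the US periods for hypothesis 2a are 2007-2011 before and 2012-2017 after, with the matched controls as comparator and a downward trend with little or no level change as the impact model. Hypothesis 2b is that the 2015 US introduction of lumacaftor/ivacaftor for F508del homozygotes lowered PERT use and DIOS incidence: "Specifically, we hypothesise a downward trend, no lag". It is confined to the US because "introduction of Orkambi was delayed in the UK until 2019".

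The only exclusion for the modulator analyses (section 4.2.2) is: "Patients whose CFTR modulator status is unknown or only have one year of CFTR data recorded on the registry will be excluded". The Objective 2 sensitivity work is a distributed lag of 1 to 3 years and a comparison with an autoregressive model.

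**The concern.** By the plan's own account, a group of patients who can serve as 2a controls gains access to a second modulator partway through the post period, and the plan expects that drug to move the same outcomes in the same direction. A controlled interrupted time series relies on the control series showing what would have happened without treatment. If part of it is treated from 2015, the control slope bends downward and the exposed-minus-control slope difference shrinks. That slope is the effect 2a specifies.

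The plan itself warns that events among exposed patients may be few, so there is little room for attenuation. In the UK this drug arrives after the data end. A weaker US result in the descriptive side-by-side reading could therefore partly reflect control contamination and be misread as a difference in drug effect.

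**Working it through.** The plan states no sample size, effect size or power, so there is no figure of its own to reproduce.

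**Overlap.** The US post years are 2012-2017, which is 6. Lumacaftor/ivacaftor is available in 2015-2017, so 3 of 6 are affected.

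**Do the planned analyses cover it?**
- The section 4.2.2 exclusion concerns unknown status or a single year of data. It does not reach a control with known status who starts a modulator later.
- In the distributed lag, lags 1 and 2 from 2012 fall in 2013 and 2014 and are unaffected. Lag 3 falls in 2015 and cannot be separated from the new drug.
- The autoregressive comparison addresses serial correlation only.

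**Size, under stated assumptions.** The documents give no homozygous share, uptake or effect. I assume:
- homozygous share of controls f = 0.30 to 0.60;
- share of those starting by 2017 u = 0.30 to 0.70;
- treated share of controls c = f × u, from 0.30 × 0.30 = 0.09 to 0.60 × 0.70 = 0.42;
- each drug builds 1/6 of its effect per year on drug, as a simple form of the downward trend hypothesised for both;
- r = lumacaftor/ivacaftor effect relative to ivacaftor, 0.5 or 1.

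With level and trend change both free, the post-period slope is the least-squares slope over 6 years. The deviations are -2.5, -1.5, -0.5, 0.5, 1.5, 2.5 and Sxx = 17.5. The true ivacaftor slope is 1/6 per year. The control pattern below is per unit of c × r.

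- Immediate uptake in 2015: 1/6, 2/6, 3/6 in 2015-2017. Slope = (0.5×1 + 1.5×2 + 2.5×3)/6/17.5 = (11/6)/17.5 = 0.1048. Relative to 1/6, k = 0.629.
- Uptake in equal thirds over 2015-2017: 1/18, 3/18, 6/18. Slope = (0.5×1 + 1.5×3 + 2.5×6)/18/17.5 = (20/18)/17.5 = 0.0635, so k = 0.381.

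Share of the slope difference hidden = k × c × r:

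| Uptake | r = 0.5 | r = 1 |
|---|---|---|
| Spread | 1.7-8.0% | 3.4-16.0% |
| Immediate | 2.8-13.2% | 5.7-26.4% |

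**Cross-check.** If each drug's first calendar year counts as zero effect, immediate uptake gives a control pattern of 0, 1, 2 and k = (1.5×1 + 2.5×2)/17.5 = 0.371. With c from 10% to 50% and r of 0.5 or 1, 2-19% of the slope is hidden, which is the same order.

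**Ending the US series at 2014.** The standard error of the trend change, in residual SD units with independent errors, is √(1/Sxx_pre + 1/Sxx_post). With 5 pre and 6 post points it is √(1/10 + 1/17.5) = 0.396. With 3 post points it is √(1/10 + 1/2) = 0.775. The ratio is 1.95.

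**The case against.** The strongest reply is that the plan never says control status is frozen at the match year. The phrase about the year of commencement attaches to representativeness, and non-user carries no date. Follow-up of controls to 2017 is likewise inferred from the 2a window. A reader might infer that the plan fixes status at matching; the text does not establish that. What stands is that the match year is the only time point given. The other reading, no use through 2017, is not stated either and would select controls on later treatment. Both readings need a rule.

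A reader might also extend the point to Objective 3 with equal force. The documents do not support that. Its comparator is no modulator, it has a separate US comparison of ivacaftor with lumacaftor/ivacaftor, and a cumulative modulator exposure sensitivity analysis may partly capture later starters. What is missing is only when status is judged.

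It is also fair to say that the bias is modest under the plan's own effect model, and that the plan rules out statistical tests between the registries. The US-UK consequence is therefore one of interpretation only.

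**Conclusion.** The gap in US 2a is real and should be closed before analysis. It goes beyond missing detail, because using the match-year pool unchanged to 2017 allows treated control time into half of the post period. If hypothesis 2b is true, the direction is toward no effect. If lumacaftor/ivacaftor has no effect on these outcomes, or few controls start it, the bias is nil or small.

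The 2-16% and 3-26% ranges rest on assumed homozygous share, uptake and relative effect, and on a trend-type action for both drugs. One could obtain figures above half of the slope by letting lumacaftor/ivacaftor act in full at once while ivacaftor builds over six years. The plan hypothesises a downward trend for both, so that asymmetry has no basis in the documents. Nor can it be said that the lag analyses are uninformative as a whole: only the third lag coincides with 2015.

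**What to change.** 1. For US 2a, state that control non-user status is set at matching and that non-use through 2017 is not required. Pre-specify one sensitivity analysis that excludes F508del homozygotes from the US control pool at matching. The primary pool stays as planned.
2. Report by year the number of matched US controls with a recorded modulator start, subject to the registries' rule on cells below five. This shows the reader how large the problem can be.
3. Optionally, show the US series ended at 2014 as a descriptive check. With 3 post points and a standard error about 1.95 times larger, it cannot serve as a test.
4. For US Objective 3, add one line: modulator status is classified by year from the recorded start dates, so that control years on lumacaftor/ivacaftor do not count as no modulator.

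The cost is a few lines of SAP text and some extra analysis. Genotype and modulator start dates are already among the requested variables. The drawback is that the pool without homozygotes may give fewer or poorer matches, so its covariate balance should be reported beside the result.

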- UK 2012-2017 & US 2012-2017 separately
 - Exposure: ivacaftor (minimum 6 months) vs No modulator (matched)
 - Secondary comparator: ivacaftor alone and lumacaftor/ivacaftor (US only)
- DIOS events:
 - Outcome: Patient-level annualised DIOS event counts
 - Multilevel Poisson Regression model for count data (or negative binomial) by year
 - Incidence rate ratio (frequency of DIOS events)
 - Adjusted analysis for main covariates (DAG – Fig 2), also include history of DIOS as pre-exposure time will not be modelled.
 - Contingency table with χ^2 /fisher if insufficient events for modelling.
- PERT usage:
 - Outcome: Patient-level annualised PERT dosage standardised by weight
 - Secondary: decreased PERT usage vs continued/increased
 - Multilevel linear regression for continuous data
 - Secondary: multilevel logistic regression for dichotomised data
 - Adjusted for main covariates (DAG – Fig 2), also include history of DIOS as pre-exposure time will not be modelled.
- Sensitivity analyses
 - CFTR modulator start year excluded, finite distributed lag (1-3 years).
 - Long run propensity (cumulative 0-3 years), cumulative modulator exposure.

Sample size and justification

N/A.- registry study

ADVERSE EVENTS

This is a registry study therefore there is no individual participant interaction and as such no associated risk or burden for participants in the study. Patient's data will be provided as anonymised data and therefore patient confidentiality will be maintained.

ETHICAL AND REGULATORY ASPECTS

ETHICS COMMITTEE AND REGULATORY APPROVALS

Requests for the data required the approval of the UK CF Trust Registry Steering Committee after reviewing of the programme development grant aims, analysis and plan for publication of results. In the US, the request for registry data was reviewed and approved by the Patient Registry/Comparative Effectiveness Research Committee and was subject to peer review.

The data will be provided from the registries as anonymised data so the individuals cannot be identified. Specifically, the CF Foundation requires that no individually identifiable information from the CF Foundation Patient Registry shall be included in publications and other written products and data must be presented in the aggregate. Both US and UK registries require that all tables or presentation of the data generated from registry data should include a patient count of five or more in each cell and any values less than 5 should be represented as <5.

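### The plan names the ATT, which needs outcome data, to assess the matching specification against alternates, and does not say that the base match is kept whatever the ATT shows

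*Combined protocol and SAP*

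**What the plan says.** In Statistical Analysis, Objective 1, item 2, the base specification is definite: "Nearest neighbour matching, caliper 0.2 standard deviation, 3:1 ratio of unexposed to exposed will be used for propensity matching". It is run by first year of exposure and uses pre-exposure information only. The purpose is also given: "Patient-level data will be used to create registry-based control groups with similar demographic features to those taking CFTR modulators".

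Two sentences then describe how the match is checked. The first is "Standardised mean difference will be used to check covariate balance between matched and unmatched populations". The second is "Average treatment effect of treated will be used to assess matching specification with alternates". The section gives no limit for the standardised mean difference (SMD), no list of alternates and no outcome for the ATT. It does not say what follows if the ATT differs between specifications.

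The matched controls are used later. Analyses 2a and 2b under Objective 2 both list "Propensity score matched controls (demographic control", and the main contrast of Objective 3 is "Exposure: ivacaftor (minimum 6 months) vs No modulator (matched". The Objective 2 sensitivity analyses cover lags of one to three years and an autoregressive model. The Objective 3 list has "CFTR modulator start year excluded, finite distributed lag (1-3 years" and cumulative exposure. Neither includes alternative matches.

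**The concern.** Whether a match is adequate is a question about covariates: do the controls resemble the exposed patients before exposure? The ATT answers a different question, because it contrasts outcomes after exposure. A poor match can give a plausible ATT and a good match a surprising one, so the ATT cannot show which specification is better.

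The sentence stands in the step that builds the controls, and no sentence closes the specification before the ATT is seen. As written, an analyst could compare effects across alternates and then settle on a control group. The hypotheses are directional (lower PERT use, fewer DIOS events), and the plan itself expects few events among exposed patients, so ATTs would be imprecise and could differ between specifications by chance.

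At stake is the demographic comparator in 2a and 2b and the main contrast in Objective 3. The pre-intervention time control, the UK parallel plot in 2b and the comparison of ivacaftor with lumacaftor/ivacaftor do not depend on it.

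**Working it through.** The plan states no sample size, alpha or power, so there is no figure of its own to reproduce. The check has three parts.

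**1. What the text settles.**
- Base match: stated as what will be used.
- Role of the ATT: to assess, not to select.
- Rule that the base match is kept regardless of the ATT: none.
- Matching alternates among the sensitivity analyses of Objectives 2 and 3: none.

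The text is compatible with a robustness comparison and with revision of the match.

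**2. How far two ATTs could differ by chance.** Assume both specifications use the same n exposed patients, each has 3n controls, variances are equal, and a share f of controls is common to both. The correlation of the two ATTs is

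rho = (1/n + f/(3n)) / (1/n + 1/(3n)) = 0.75 + 0.25f.

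The SD of their difference, in units of one ATT's standard error (SE), is sqrt(2(1 − rho)).

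| f | rho | SD of difference |
|---|---|---|
| 0 | 0.75 | 0.71 SE |
| 0.5 | 0.875 | 0.50 SE |
| 0.8 | 0.95 | 0.32 SE |

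The identical exposed set is an assumption, since changing the caliper can drop exposed patients. With 90% of exposed patients and 50% of controls shared, rho = (0.9 + 0.5/3) / (1 + 1/3) = 0.80 and the SD is sqrt(0.40) = 0.63 SE. The table is therefore not an upper range.

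**3. What selection would cost, if it happened.** Take k specifications with no true effect and z-statistics equally correlated at rho, and keep the most favourable. One-factor integration gives P(min z < −1.96), the expected minimum, and the coverage of the kept 95% confidence interval:

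| k | rho | False benefit | Mean shift | Coverage |
|---|---|---|---|---|
| 2 | 0.95 | 3.2% | −0.13 SE | 95.0% |
| 2 | 0.875 | 3.6% | −0.20 SE | 95.0% |
| 3 | 0.95 | 3.7% | −0.19 SE | 94.8% |
| 3 | 0.875 | 4.4% | −0.30 SE | 94.6% |

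The reference is 2.5%. At k = 1, the base match kept, it is exactly 2.5%. An extreme case, six specifications sharing no controls (rho 0.75), gives 7.6%, −0.63 SE and 92.2%.

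**The case against.** The strongest reply is that no error is shown, only a missing prohibition. The plan fixes one specification and says it will be used. Assessing it with alternates is most naturally a robustness check, and such a check is reasonably written beside the match. A reader might infer that the plan selects its control group by the treatment effect. The documents do not support that: the verb is assess, a base match is named, and matching is confined to pre-exposure information. This stands, and it limits the point to a gap in pre-specification.

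A reader might also infer that balance will be checked on the wrong groups, because the SMD sentence contrasts matched with unmatched populations. The stated aim of controls resembling modulator users makes before versus after matching the likely meaning. That sentence needs clearer wording and no more.

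The numbers are also fairly criticised as hypothetical. They need selection, a number of alternates, an overlap and an alpha that the plan does not give, and they assume that the ATT's behaviour carries over to segmented regression and multilevel models. In the milder cases coverage is almost nominal. This stands too, so the figures are illustration only. Objective 3's adjustment for covariates and history of DIOS reduces measured confounding, but would not undo a match revised after the effect was seen.

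What the reply does not remove is that an outcome-based quantity is the stated means of assessing the matching specification, with no sentence protecting the base match.

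**Conclusion.** The point holds as a gap in pre-specification that should be closed. It is not evidence of outcome-driven selection. The ATT is the wrong instrument for judging a match, and the text leaves room to revise the comparator of Objectives 2 and 3 after seeing the effect.

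The size is zero if the base match is kept. If the most favourable of 2 to 3 matches sharing 50% to 80% of their controls were kept, false benefit would be about 3.2% to 4.4% against 2.5%. That range is conditional on the assumptions set out above, including selection itself. No size is claimed for the SMD wording. Confidence is medium, because the authors may intend only a robustness comparison.

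**What to change.** Replace the two checking sentences in Objective 1, item 2 with text to this effect:

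1. The nearest-neighbour match with 0.2 SD caliper and 3:1 ratio is the primary specification.
2. Its adequacy is judged only on SMDs between exposed and unexposed patients before matching, and between exposed patients and matched controls after matching, against a limit stated in advance (for example 0.1). Post-exposure DIOS and PERT outcomes are not used. Pre-exposure history may still be matched on.
3. If the limit is not met, the next alternate in a pre-listed order is taken, on balance alone. The number of exposed patients retained is reported but does not drive the choice, so balance and retention need not be traded off.
4. The ATT, with its outcome named, is reported across the alternates as sensitivity analysis only, and is added to the sensitivity analyses under Objectives 2 and 3.

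The cost is a short edit and a brief ordered list of alternates; no extra data are needed. The downside is that outcomes arrive in the same registry files, and Objective 1, item 1 describes them before matching. Keeping them out of the matching step therefore relies on analyst discipline, for example a matching file without the post-exposure outcome columns.
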